13.1. Definition of an Adverse Event (AE) and AE's reporting

The main criterion for tolerability is the occurrence of toxicities and Adverse Events (AEs). [REDACTED]

[REDACTED]

[REDACTED]

[REDACTED]

[REDACTED]

[REDACTED]

An adverse event can therefore be any of the following:

Any unfavorable and unintended sign (including an abnormal laboratory finding) (see **NOTE 1** below), symptom, or disease temporally associated with the use of a medicinal product, whether or not considered related to the medicinal product.

Any new disease or exacerbation of an existing disease (a worsening in the character, frequency, or severity of a known condition), except events that are clearly consistent with the expected pattern of the disease progression. These data will be captured as efficacy assessment data only. If there is any uncertainty as to whether an event is due to disease progression, it should be reported as an adverse event.

Recurrence of an intermittent medical condition (e.g., headache) not present at baseline.

Any deterioration in a laboratory value or other clinical test (e.g., ECG, X-ray) that is associated with symptoms or leads to a change in study treatment or concomitant treatment or discontinuation from study drug.

Adverse events that are related to a protocol-mandated intervention, including those that occur prior to assignment of study treatment (e.g., screening invasive procedures such as biopsies).

Adverse events that occur during or within 24 hours after study drug administration and are judged to be related to study drug infusion should be captured as a diagnosis (e.g., "infusion-related reaction" or "anaphylactic reaction") on the Adverse Event eCRF. If a patient experiences both a local and systemic reaction to the same dose of study drug, each reaction should be recorded separately on the Adverse Event eCRF. Associated signs and symptoms should be recorded on the dedicated Infusion-Related Reaction eCRF.

A pre-existing medical condition should be recorded as an adverse event only if the frequency, severity, or character of the condition worsens during the study (e.g., "more frequent headaches").

NOTE 1: Abnormal laboratory and vital signs values:

A laboratory test result must be reported as an adverse event if it is a change from baseline and meets any of the following criteria:

Is accompanied by clinical symptoms,

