Results in a change in study treatment (e.g., dosage modification, treatment interruption, or treatment discontinuation),

Results in a medical intervention (e.g., potassium supplementation for hypokalemia) or a change in concomitant therapy,

Is clinically significant in the investigator's judgment.

If a clinically significant laboratory abnormality is not a sign of a disease or syndrome, the abnormality itself should be recorded on the Adverse Event eCRF, along with a descriptor indicating if the test result is above or below the normal range (e.g., "elevated potassium").

A vital sign result must be reported as an adverse event if it is a change from baseline and meets any of the following criteria:

Is accompanied by clinical symptoms,

Results in a change in study treatment (e.g., dosage modification, treatment interruption, or treatment discontinuation),

Results in a medical intervention or a change in concomitant therapy,

Is clinically significant in the investigator's judgment.

If a clinically significant vital sign abnormality is a sign of a disease or syndrome (e.g., high blood pressure), only the diagnosis (i.e., hypertension) should be recorded on the Adverse Event eCRF.

The finding of an elevated ALT or AST ($> 3 \times$ baseline value) in combination with either an elevated total bilirubin ($> 2 \times$ ULN) or clinical jaundice in the absence of cholestasis or other causes of hyperbilirubinemia is considered to be an indicator of severe liver injury. Therefore, investigators must report as an adverse event the occurrence of either of the following:

Treatment-emergent ALT or AST $> 3 \times$ baseline value in combination with total bilirubin $> 2 \times$ ULN (of which $\geq 35\%$ is direct bilirubin),

Treatment-emergent ALT or AST $> 3 \times$ baseline value in combination with clinical jaundice.

This abnormal laboratory values related to the liver function should be recorded on the Adverse Event eCRF and reported immediately as a SAE (AESI).

The severity will be classified according to the NCI CTCAE Version 5.0. The CTCAE is available for downloading on the internet (see appendix 1).

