[REDACTED], regardless of whether it is considered related or not to the study drug and that, at any dose, results in any of the following:

- results in death (fatal)
- is life-threatening (defined as an event in which the participant was at risk of death at the time of the event; it does not refer to an event which hypothetically might have caused death if it was more severe)
- requires inpatient hospitalization or causes prolongation of existing hospitalization (see **NOTE 2** below)
- results in persistent or significant disability/incapacity
- is a congenital anomaly/birth defect
- is an important medical event. Defined as a medical event(s) that may not be immediately life-threatening or result in death or hospitalization but, based upon appropriate medical and scientific judgment, may jeopardize the subject or may require intervention (e.g., medical, surgical, laboratory abnormal parameters...) to prevent one of the other serious outcomes listed in the definition above (see **NOTE 3** below)

After informed consent has been obtained, but prior to initiation of study drug, only serious adverse events caused by a protocol-mandated intervention (e.g., invasive procedures such as biopsies, discontinuation of medications) should be reported.

Seriousness is based on patient/event outcome or action criteria usually associated with events that pose a threat to a patient's life or functioning. Seriousness (not severity) serves as a guide for defining regulatory reporting obligations

NOTE 2: The following hospitalizations are not considered SAEs:

- A visit to the emergency room or other hospital department < 24 hours, that does not result in admission, except if it is considered as an important medical event or life- threatening
- elective surgery which has been planned prior to signing consent

- routine health assessment requiring admission for baseline/trending of health status (e.g., routine colonoscopy)
- admissions as per protocol for a planned medical/surgical procedure
- admission for administration of anticancer therapy in the absence of any other SAEs
- admission encountered for another life circumstance that carries no bearing on health status and requires no medical/surgical intervention (e.g., lack of housing, economic inadequacy, caregiver respite, family circumstances, administrative reason)

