- progression of disease. By convention, clinical events related to the primary cancer being studied or to the primary cancer progression are not to be reported as SAEs, even if they meet any of the seriousness criteria from the standard SAE definition, unless the event is more severe than expected and therefore the investigator considers that their clinical significance deserves reporting.

NOTE 3: Any laboratory abnormalities should be documented as a SAE if:

- Intensive treatment in an emergency room or at home for allergic bronchospasm is needed,
- Blood dyscrasias or convulsions that do not result in hospitalization,
- Any untoward event related, and unexpected, to the protocol procedures,
- The laboratory test result is clinically significant or meets the definition of a SAE,
- The laboratory abnormality required the participant to have study drug discontinued or interrupted,
- The laboratory abnormality required the subject to receive specific corrective therapy.

A SAE report should be completed for any event where doubt exists regarding its seriousness. Although overdose, pregnancy, AESI (e.g., potential drug-induced liver injury (DILI)), important medical event, and cancer (secondary malignancy) are not always serious by regulatory definition, these events must be handled as SAEs. If applicable, SAEs must be collected that relate to any later protocol-specified procedure (e.g., a follow-up skin biopsy).

If the investigator believes that a SAE is not related to study drug but is potentially related to the conditions of the study (such as withdrawal of previous therapy or a complication of a study procedure), the relationship should be specified in the narrative section of the SAE Report Form and an important medical event would be the seriousness.

All deaths that occur during the reporting period that are clearly the result of disease progression should not be reported as a SAE, but they should be collected as an AE. All deaths where it is not due to disease progression and deaths with an unknown cause should always be reported as a SAE.

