13.4. Overdose and secondary malignancies

An overdose is defined as the accidental or intentional administration of any dose of a product that is considered both excessive and medically important. All occurrences of overdose must be reported as a SAE, indicating "life-threatening" as the seriousness.

Secondary malignancies are not always serious by regulatory definition, these events must be handled as SAEs.

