13.5. SAEs and SUSARs reporting

All SAEs that occur within **30** days of the last administered study medication must be collected. Any SAE must be reported by submitting the completed Initial SAE Form in the online eCRF within 24 hours of awareness, even if they do not meet any of the seriousness criteria.

In case of the eCRF is unavailability, the submission could be done by sending the SAE form preferably by email to [contact] or by fax to the Fundación GECP (SLCG/GECP) Pharmacovigilance Office: [contact]. An appropriate SAE form (see appendix 3) should be used to report SAEs to Fundación GECP (SLCG/GECP). The paper SAE form has to be sent within the timeline period for reporting of 24 hours of awareness. **Once the eCRF system is available again, the SAE has to be completed and submitted by the site into the eCRF.**

If only limited information is initially available, a follow-up report is required to complete the information as soon as possible. (Note: Follow-up SAE reports should include the same SAE term(s) initially reported.)

The SAE outcome must be reported within 14 days after initial reporting by submitting the Follow up SAE Form in the online eCRF. In case the SAE is reported as ongoing after 14 days, a follow-up report has to be submitted again with the final outcome.

If an ongoing SAE changes in its grade, relationship to study drug, seriousness, SAE term or if new information becomes available, a new follow-up SAE report should be sent within 24 hours to the Fundación GECP (SLCG/GECP) using the same procedure after described.

Any SUSAR occurred during the trial will be notified under Spanish clinical regulation to the principal investigators, to the Health Authority (AEMPS) via Eudravigilance within the timelines specified in the Royal Decree 1090/2015 on clinical trials regarding the recording, evaluation and reporting of adverse events. Also, the autonomous regions will be informed about all SUSARs according to the current Spanish clinical trial regulation.

For any doubt please contact Fundación GECP (SLCG/GECP) pharmacovigilance office by this email: [contact] or by the [contact].

Also, Fundación GECP (SLCG/GECP) will ensure that all SAEs, SUSARs, AESIs and pregnancy reports in the clinical database (eCRF) are reported to the authorization holder y during the conduct of the study including periodic reconciliation.

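### The overdose coding rule and the laboratory triggers in NOTE 3 contradict the protocol's own definition of a serious adverse event

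*Combined protocol and SAP*

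**What the plan says.** **Overdose.** Section 13.4 defines an overdose as a dose that is both excessive and medically important. It then states: "All occurrences of overdose must be reported as a SAE, indicating" the life-threatening category as the seriousness. In Section 13.2 an event meets that criterion if it "is life-threatening (defined as an event in which the participant was at risk of death at the time of the event"; the same bullet excludes events that could only hypothetically have been fatal. The text after NOTE 3 lists overdose among the events that are not always serious by regulatory definition but are to be handled as SAEs. The SAE form (Appendix 3) has code 7 for a non-serious AESI and code 8 for a non-serious secondary malignancy.

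**Laboratory abnormalities.** NOTE 1 in Section 13.1 sets out when a laboratory change is an AE. One of its four criteria is "Results in a medical intervention (e.g., potassium supplementation for hypokalemia) or a change in concomitant therapy". NOTE 3 in Section 13.2 sets out when a laboratory abnormality is documented as an SAE. Its triggers include "The laboratory abnormality required the participant to have study drug discontinued or interrupted" and "The laboratory abnormality required the subject to receive specific corrective therapy", and also a result that is clinically significant or meets the SAE definition. NOTE 3 is called from the important-medical-event bullet. That bullet asks for medical and scientific judgment that the event may jeopardize the subject, or may need intervention to prevent another of the listed serious outcomes.

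**Reporting.** Section 13.5 requires SAE submission within 24 hours, "even if they do not meet any of the seriousness criteria".

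**The concern.** A seriousness code should record which criterion in the definition an event met. Both rules break that link. The overdose rule assigns one particular criterion whatever happened to the patient. The laboratory rule accepts as serious what NOTE 1 treats as sufficient only for an AE.

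Safety and tolerability is a secondary objective, and SAE counts will be read alongside the graded AEs. If events that meet no seriousness criterion are counted, the SAE figures no longer mean what Section 13.2 says they mean. There is also a regulatory consequence. Under Section 13.2 an SAE judged related is a serious adverse reaction and, if unlisted, a SUSAR that goes to the health authority. A non-serious laboratory event made an SAE by NOTE 3 can enter that route.

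**Working it through.** No arithmetic decides this point, and the plan states no figure to reproduce. The check is a comparison of the rules.

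**Step 1: NOTE 1 against NOTE 3.**

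| NOTE 1: laboratory change is an AE if | NOTE 3: laboratory abnormality is an SAE if | Recurs? |
|---|---|---|
| "Is accompanied by clinical symptoms" | no counterpart | No |
| "Results in a change in study treatment (e.g., dosage modification, treatment interruption, or treatment discontinuation" | study drug discontinued or interrupted | Yes, except dose modification without interruption |
| medical intervention or changed concomitant therapy | specific corrective therapy needed | Yes for corrective treatment; NOTE 1 is somewhat wider |
| investigator judges it clinically significant | clinically significant, or meets the SAE definition | Yes; the word or makes clinical significance enough by itself |

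Three of the four AE criteria therefore reappear as sufficient for an SAE. NOTE 1's own example, potassium given for hypokalemia, meets the corrective-therapy trigger in NOTE 3.

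**Step 2: NOTE 3 against the bullet it annotates.** Under the important-medical-event bullet, an intervention counts if it may be needed to prevent another serious outcome. In NOTE 3 any specific corrective therapy counts, and so does any interruption. NOTE 3 does not repeat the bullet's condition.

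**Step 3: can the triggers fire in this trial?** Yes, because the protocol itself directs such holds. In Section 11.2, the paragraph on Grade 4 immune-related lymphopenia describes an AE that consists of one isolated abnormal value with no clinical counterpart, and has treatment held until the cause is known. The bleeding table in the same section withholds treatment after a hemoglobin fall of more than 2.0 g/dL over two weeks. Each hold is an interruption for a laboratory abnormality, so NOTE 3 makes it an SAE whether or not any Section 13.2 criterion is met.

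**Step 4: overdose.** Take an overdose that is excessive and medically important but carries no actual risk of death.

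- Section 13.4: code life-threatening.
- Section 13.2 definition: not life-threatening.
- Section 13.2, text after NOTE 3: possibly not serious at all.
- Appendix 3: non-serious codes for AESI and secondary malignancy, none for overdose.

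No entry satisfies all four.

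**Step 5: scale.** The documents give no expected SAE rate, laboratory-event rate or overdose rate. Assume that all 47 planned patients are treated. A patient whose only SAE is a NOTE 3 laboratory event then adds 1/47 = 2.1 percentage points to SAE incidence. For assumed counts of 5, 10 and 20 such patients:

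- 5/47 = 10.6 points
- 10/47 = 21.3 points
- 20/47 = 42.6 points

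These counts are illustrations, not forecasts.

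**The case against.** The strongest defense is that broad capture looks intended. Section 13.2 asks for an SAE report wherever seriousness is in doubt, and it lists events to be handled as SAEs although they are not always serious. NOTE 3 hangs from the important-medical-event bullet, so a site could read it as subject to that bullet's judgment. Sending overdoses or selected laboratory events to the sponsor quickly is legitimate; Section 13.1 already does so for combined liver abnormalities. This defends rapid reporting. It does not defend recording a criterion that was not met, and NOTE 3 as written carries no judgment condition.

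Several stronger readings are tempting, but the documents do not support them:

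- **Sites will split between NOTE 1 and NOTE 3.** The notes answer different questions: whether an event is an AE, and whether it is an SAE. Section 13.1 requires an AE entry for every SAE, so one event can satisfy both.
- **The SAE rate is a main safety result and will be inflated by a known amount.** The objective in Section 4.2 is AEs graded by CTCAE; no SAE-rate endpoint is stated, and any specific inflated rate rests on invented inputs.
- **The severity profile is misstated.** Sections 13.1 and 13.2 keep severity and seriousness apart, so a wrong seriousness code leaves the grade unchanged.
- **The life-threatening code is what brings an overdose into SUSAR assessment.** That follows from handling it as an SAE and judging it related.
- **The Section 13.5 phrase on seriousness criteria is a further error.** Section 13.3 sends AESIs to Section 13.5 even when they are not serious, and form codes 7 and 8 exist for such reports. The phrase supports them.

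Two limits also stand. The study's AESI list is redacted, so one cannot tell how many laboratory events would be expedited anyway. The overdose miscoding arises only if an overdose without risk of death occurs, and dosing is a fixed 1200 mg infusion in a monitored setting.

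**Conclusion.** The point holds as an internal contradiction. Section 13.4 conflicts with the life-threatening criterion and with the form's codes. NOTE 3 conflicts with the important-medical-event test it is meant to explain. Applied as written, the rules yield seriousness codes and SAE counts that do not match the protocol's own definition.

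The direction for laboratory events is upward, and the amount is unknown. The 2.1 points per patient assumes 47 treated patients and no other SAE in the patient concerned. The overdose part is conditional on such an event occurring. The effect is confined to safety classification and reporting: the PFS analysis, the sample size and the CTCAE grades do not change.

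**What to change.** 1. **Section 13.4.** Keep 24-hour reporting of every overdose on the SAE form, but replace the mandatory life-threatening code with the seriousness code that actually applies.
2. **Appendix 3 and eCRF.** Add a non-serious overdose code beside codes 7 and 8.
3. **Section 13.2, NOTE 3.** State that clinical significance, interruption or discontinuation of study drug, and corrective therapy make a laboratory abnormality an SAE only when the event also meets a Section 13.2 criterion, including the important-medical-event test. Otherwise they remain AE criteria under NOTE 1.
4. **Section 13.5.** Leave the wording as it is, so that non-serious AESIs, overdoses and secondary malignancies still arrive within 24 hours.

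The cost is amendment wording and one added code. The downside is that fewer routine laboratory events reach the sponsor within 24 hours; they are still recorded as AEs within the 5 days set in Section 13.1.

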8.1.4. Progression Disease

When the progression disease will be confirmed by mRECIST criteria and/or by principal investigator judgement these samples are strongly recommended to be collected:

- Tumor tissue from a rebiopsy, if clinically feasible and patient accepts this procedure
- Blood samples
- Pleural effusion liquid (when feasible)

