| Trial Medication (Generic name/Brand name) | Dose and units | Route (IV, PO, SC...) | Date of administration before SAE | Action taken ¹ | Stopped the event when the medication was discontinued ² | The event returned when the medication is resumed ³ |
|--|----------------|-----------------------------|--------------------------------------|------------------------------|--|---|
| | | | | | | |
| | | | | | | |
| | | | | | | |

IS THERE ANY OTHER EXPLANATION OR CAUSE FOR THE ADVERSE EVENT?

CONCOMITANT DISEASE POSSIBLE RELATION WITH CONCOMITANT DRUGS STUDY PROCEDURES NOT APPLICABLE OTHERS (SPECIFY) _____

⁴ Action taken with regard to trial medication: 0: none; 1: Reduced; 2: Delayed; 3:Delayed and Reduced; 4: permanent discontinuation; 5: other (specify):

^aStopped or returned the adverse event when the medication was discontinued or resumed? 0: YES; 1: NO; 2: Not applicable

PREVIOUS RELEVANT MEDICAL HISTORY

PREVIOUS RELEVANT MEDICAL HISTORY (PREVIOUS DIAGNOSIS, SURGERIES, ALLERGY, PREGNANCIES, CONCOMITANT DISEASES, ETC):

CONCOMITANT MEDICATION (Medication taken by the patient due to basal diseases or supportive Clinical trial medication)

* Prescription reason: 1: Regular medication/baseline conditions; 2: Concomitant Medication/prophylaxis; 3: Adverse event; 4: Other (specify)

INFORMATION ABOUT THE SPONSOR AND THE PRINCIPAL INVESTIGATOR (PI) OF THE TRIAL

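### Section 13.2 sets seriousness by cause for SAEs tied to study conditions but not to the drug, so a hospitalised or life-threatening procedure complication would be coded as an important medical event

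*Combined protocol and SAP*

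**What the plan says.** Section 13.2 lists the SAE criteria and applies them whether or not the event is thought to be drug-related. One criterion is that the event "requires inpatient hospitalization or causes prolongation of existing hospitalization". Another is the important medical event: "Defined as a medical event(s) that may not be immediately life-threatening or result in death or hospitalization". The section adds that seriousness rests on outcome or action criteria and serves as a guide to regulatory reporting obligations.

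Later in the same section comes a special rule. Its condition is: "If the investigator believes that a SAE is not related to study drug but is potentially related to the conditions of the study". The examples given are withdrawal of previous therapy and a complication of a study procedure. The instruction is: "the relationship should be specified in the narrative section of the SAE Report Form and an important medical event would be the seriousness".

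The SAE form (Appendix 3) has a seriousness key with 1 for death, 2 for life-threatening, 3 for hospitalisation and 6 for medically significant. It also has a grade (1-5), an outcome (3 = fatal) and a causality code that refers to study drugs only. A separate item asks about any other explanation or cause, and its options include "STUDY PROCEDURES NOT APPLICABLE OTHERS".

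**The concern.** The general criteria ask what happened to the patient. The special rule asks what caused the event and then fixes the answer. When both apply, they give different codes for the same event.

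The trial adds invasive research procedures to which the rule would apply. A pleural tap is planned at baseline and at progression in patients with an effusion (Section 1, Translational research). Section 8.1.4 strongly recommends further sampling at progression, including "Tumor tissue from a rebiopsy, if clinically feasible and patient accepts this procedure". If one of these leads to an admission or a life-threatening event, the seriousness field would show the class meant for events that met none of the more severe criteria. Anyone who later counts hospitalised or life-threatening SAEs by that field would miss it.

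The period before the first dose is the most exposed. Section 13.2 says that between consent and first dose "only serious adverse events caused by a protocol-mandated intervention" should be reported. None of these can be related to a drug not yet given, so the special rule would reach all of them.

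**Working it through.** No sample size, error rate or event figure enters this point, and the plan states no figure to reproduce. The check sets the texts side by side and follows one event through the form.

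**Step 1: what decides seriousness.** The general text of Section 13.2 uses outcome or action criteria. Its important-medical-event criterion covers events that "may not be immediately life-threatening or result in death or hospitalization but, based upon appropriate medical and scientific judgment", may put the subject at risk or need intervention to prevent one of the other listed outcomes. That makes it the residual class. The special rule uses cause alone and states no exception for events that meet another criterion.

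**Step 2: whom the rule covers.** It covers only SAEs that the investigator judges not related to study drug and potentially related to study conditions. A procedure complication that is also judged drug-related falls outside it.

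**Step 3: the form when the rule is followed literally.**

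| Complication, not drug-related | Code by the general criteria | Code by the special rule | Other structured field on the form |
|---|---|---|---|
| Hospitalised | 3 | 6 | None |
| Life-threatening | 2 | 6 | Grade 4, approximate only |
| Fatal | 1 | 6 | Outcome 3, or grade 5 |
| None of the other criteria, but medically important | 6 | 6 | Not needed |

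Grade 4 is only approximate because Section 13.1 says that severity grade does not reflect clinical seriousness.

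**Step 4: whether the cause can be recovered.** The item on another explanation or cause has a study-procedures option, so procedure-related SAEs can be tabulated if sites tick it. Withdrawal of previous therapy has no option of its own and would go under the free-text others option. The item appears once per form although several SAE terms can be listed, so linking a cause to a term may be ambiguous.

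**Step 5: what depends on the seriousness code.**
- The safety objective (Section 4.2) uses CTCAE grade, and Section 13.1 requires an AE entry for every SAE notified.
- Section 13.5 sets 24 hours for any SAE, whatever its code.
- SUSAR assessment (Section 13.2) starts from drug-related SAEs, which the rule excludes.
- PFS does not use the code.

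**Step 6: how many events.** One rebiopsy and two taps in each of 47 patients would be 47 x 3 = 141 procedures. This is not a usable forecast, because taps depend on an effusion and on feasibility, and rebiopsy depends on feasibility and the patient's agreement. It also leaves out any new biopsy at entry where archival tissue is too old. The documents give no complication rate. As the last row of the table shows, some serious complications would be coded 6 correctly.

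**The case against.** The best defence is that the sentence is a fallback: it makes sure that an event caused by study conditions counts as serious when no other criterion applies. NOTE 3, attached to the important-medical-event criterion, lists unexpected untoward events related to protocol procedures. The definition also says only that such an event may not be life-threatening or lead to admission, which is not a strict exclusion. This reading is possible but weak. The sentence starts from an event that is already an SAE and so already meets a criterion. NOTE 3 supplies the fallback without it. And Section 13.4 presets a seriousness for every overdose, so the protocol does assign codes by event type, and sites could fairly take this sentence the same way.

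A second defence is that the paper form is used only when the eCRF is unavailable (Sections 13.5 and 15), and the eCRF layout is not shown. That stands as a limit. The eCRF may hold a hospitalisation field, and the form does not say whether more than one seriousness code may be entered.

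A reader might also infer more than the documents support:
- **That procedure harms could not be counted apart from other SAEs.** The study-procedures option contradicts this.
- **That deaths would be hidden.** Outcome and grade show them, and Section 13.2 requires deaths not due to progression, or of unknown cause, to be reported as SAEs.
- **That the safety objective would understate harm.** It is based on grade, and no table by seriousness code is planned anywhere in the documents.
- **That all SAEs before the first dose would be miscoded.** They would all receive code 6, but those that meet no other criterion would be coded correctly. Section 8.1.5 also asks for SAEs to be recorded from consent, without the restriction to procedures.

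**Conclusion.** The instruction is wrong as written: it contradicts the outcome-based criteria of its own section and the separate codes on the SAE form. Among SAEs judged unrelated to study drug, a hospitalised procedure complication would be coded 6 instead of 3, and a life-threatening one 6 instead of 2. The real losses are hospitalisation, which has no other structured field on the form shown, and a reliable marker of life threat.

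Severity is minor. The number of events affected cannot be derived from the documents and is likely small in a trial of 47 patients with largely optional procedures. The primary analysis, the graded safety endpoint and the reporting timelines do not change. The conclusion assumes that sites follow the sentence literally and enter one code per event, and that the eCRF carries the same fields as the paper form.

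**What to change.** In Section 13.2, delete the closing clause of the special rule, which assigns the seriousness. State instead that seriousness follows the Section 13.2 criteria whatever the cause, and that important medical event is used only when no other criterion is met. Direct sites to record the relationship in the existing cause item of the SAE form, under study procedures or others (specify), as well as in the narrative.

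The cost is one sentence in the protocol and one line in the SAE completion instructions. The paper form needs no new field; the sponsor should confirm that the eCRF carries the same item. Some SAEs would move to a more severe seriousness class, which is the intended effect.
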